## Description of the data to be collected and what statistical procedures will be used to answer the hypothesis and research question.

Day prior to abortion: We will collect contact information, baseline demographics and history (age, BMI, race, education, indication for abortion, parity, mode of prior deliveries, prior abortion, prior osmotic dilators, number of weeks gestation, prior cervical procedures, prior surgeries, medical problems, medications, allergies). We will record baseline pain prior to positioning patient for cervical preparation. We will collect information on initial digital cervical exam (dilation/effacement/consistency/position), time of osmotic dilator or balloon placement, number of Dilapan-S if applicable, dilator placement duration, provider ease of placement by VAS, participant reported pain after procedure (within 5 minutes of speculum removal) by VAS, reported maximum pain during procedure by VAS. If digoxin is administered, it will only be done after dilator placement and all pain levels are collected.

Day of abortion. Preoperative information will also include maximum reported pain overnight prior to misoprostol administration, time of misoprostol intake, documentation of time of osmotic dilator or Foley balloon removal or expulsion (total time with dilator in place), symptoms overnight, reported maximum pain overnight by VAS, reported number of ibuprofen and Norco pills taken overnight, patient satisfaction by VAS, and if they would recommend their type of dilation for future patients.

Abortion: We will record digital cervical exam (dilation/effacement/consistency/position), need for additional mechanical dilation, total duration of procedure (speculum insertion to removal), time from insertion of first intrauterine instrument (suction cannula or forceps) to final removal of intrauterine instrument (suction cannula), type of anesthesia, primary surgeon level (senior resident in their last half of final year, fellow, faculty), surgeon satisfaction with dilation by VAS, surgeon's ease with procedure by VAS, EBL, complications (cervical laceration, hemorrhage, perforation, infection, intact expulsion).

Post procedure: Prior to discharge, at least 60 minutes but before 120 minutes after procedure (time to be recorded), participants will be asked about overall experience by VAS, and current and maximum pain since procedure by VAS.

Table 1: Cervical preparation protocol based on gestational weeks

Gestational weeks	Misoprostol (400mcg buccal 2-3h prior to D&E)	Mifepristone (200 mg PO within 1h prior to dilator placement)	# of Dilapan-S	Digoxin
18 – 19w6d	Yes	Yes	2-3	By request
20 – 21w6d	Yes	Yes	3-4	By request
22 – 23w6d	Yes	Yes	4-5	Offered

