## **Protocol**

	Fe	lle	ow	:		,	MD
--	----	-----	----	---	--	---	----

Fellowship site: Stanford University

Fellowship Director: , MD MS

Additional Research Mentors:MD MPH;MD MSH;MD MSHP;, MD MS;

Project Title: Transcervical Balloon compared to Osmotic Dilators prior to Surgical Abortion: a Non-Inferiority Randomized Trial

We will conduct an unblinded, randomized, non-inferiority trial of 40 participants undergoing second trimester abortion between 18 and 23 weeks of gestation at Stanford Health Care. Participants will be approached during their initial consultation for abortion, after consent for the abortion has been obtained. They will sign consent and be randomized on the day of cervical preparation, one day prior to their D&E. We will use 1:1 randomization using a computer-generated variable block sequence to ensure balance of treatment groups.

We will include participants of at least 18 years of age presenting to clinic for second trimester abortion at 18 to 23 weeks and 6 days gestation confirmed by ultrasound (which will include 17 weeks and 6 days gestation on day of cervical preparation, one day prior to D&E, with or without digoxin). We will include participants who are able to provide informed consent and comply with study protocol, English or Spanish-speaking, and a candidate for outpatient cervical preparation. Exclusion criteria will include anyone with an allergy to misoprostol, mifepristone or any study medication, premature rupture of membranes, intrauterine fetal demise, placenta previa, suspected abnormal placentation or evidence of infection at the time of enrollment. Participants will be excluded on day of cervical preparation, after randomization, if their initial cervical exam is 2cm dilated and 50% effaced or more.

Participants randomized to the osmotic dilator group will receive between 2 to 5 Dilapan-S using Table 1 as guidance, depending on gestational age. Those randomized to the Foley balloon group will have a Foley catheter inserted until the balloon lies beyond the internal os that will be filled with 30 mL of sterile water or saline.

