Placement of balloon or osmotic dilators will be performed in dorsal lithotomy position, with use of a speculum, standard 10-12mL paracervical block, and tenaculum or atraumatic grasper with use of adjunct initial dilation if needed (ie: os finder, sound). Adjunctive medications will be used based on our cervical preparation protocol (Table 1). Participants will receive mifepristone 200mg orally within 1 hour of osmotic dilator/balloon placement. All participants will receive misoprostol 400 ug buccal 2-3 hours prior to their scheduled D&E. Per our institutional practices, participants over 22 weeks gestation will be offered digoxin for feticide, administered upon request in earlier gestations, and use will be recorded. If the participant receives digoxin, it will be administered after dilator placement, and after the participant is asked about their pain level. Although downward traction applied to the balloon

has been associated with a shorter time to expulsion, it has been associated with more pain and bleeding.. Given these unfavorable effects, and the potential challenges of maintaining downward traction as an outpatient, initial gentle traction will be applied with the catheter taped to the participant's medial thigh; however, participants will not be instructed to maintain tension as an outpatient.

Our primary outcome will be procedure duration (speculum insertion to removal). Prior studies have demonstrated that procedure time is normally distributed with a standard deviation of 5 minutes. We will define 5 minutes as our non-inferiority threshold. To achieve 80% power with a one-sided alpha 2.5% to detect this difference, we require 16 participants per group and 32 total. Anticipating loss to follow up, we will plan to enroll 20 participants per group.

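### Does leaving the choice of D&E operator undescribed, in an unblinded trial of procedure duration, bias the primary comparison?

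*Combined protocol and SAP*

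**What the plan says.** The Protocol's opening paragraph sets out the design: "We will conduct an unblinded, randomized, non-inferiority trial of 40 participants". On timing it says: "They will sign consent and be randomized on the day of cervical preparation, one day prior to their D&E". The arm can therefore be known to the team before the D&E starts. Allocation is in variable blocks at 1:1, and no stratification factor is named: "We will use 1:1 randomization using a computer-generated variable block sequence to ensure balance of treatment groups".

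The outcome paragraph of the Protocol states: "Our primary outcome will be procedure duration (speculum insertion to removal". It uses an SD of 5 minutes, a margin of 5 minutes, a one-sided alpha of 2.5% and 80% power, giving 16 per group. It then adds: "Anticipating loss to follow up, we will plan to enroll 20 participants per group".

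Operator level appears once, under Abortion in the data section, as an item to record: "primary surgeon level (senior resident in their last half of final year, fellow, faculty". That section is headed "Description of the data to be collected and what statistical procedures will be used to answer the hypothesis and research question", but only data items follow. No primary model, covariate or operator-assignment rule is given anywhere.

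**The concern.** Randomization balances what is settled before allocation. Here the operator is not shown to be settled by then, the arm is open, and the operator's speed feeds directly into the primary outcome. If a unit gave the less familiar device to its faculty, the balloon arm would look faster for reasons unrelated to the device. If it gave those cases to trainees, the balloon arm would look slower. The first could produce a false claim of non-inferiority and the second could hide a true one. With 16 to 20 per arm, a few reassigned cases move the mean. Since the plan records operator level and gives it no analytic role, it seems at first to have seen the issue and left it open.

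**Working it through.** **Inputs from the Protocol's outcome paragraph.** SD 5, margin 5, one-sided 2.5%, 80% power, 16 per group needed, 20 enrolled. The implied true difference is 0.

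**The plan's own figure.** n per group = 2 × (1.960 + 0.842)² × (5/5)² = 15.70, rounded up to 16. This reproduces. Standard errors are 5 × √(2/16) = 1.768 and 5 × √(2/20) = 1.581 minutes. Power by the noncentral t is 78% at 16 per arm and 87% at 20.

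**Operator chosen without regard to arm.** Chance imbalance is expected. If half of cases go to each level, the SD of the between-arm difference in proportions is √(2 × 0.25/20) = 0.158, or 16 points, at 20 per arm. If the SD of 5 already includes operator variation, this imbalance is part of the standard error. Simulation with operators independent of arm (gaps of 3 and 5 minutes, 16 and 20 per arm) gives an unadjusted type I error of 2.5%.

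**Operator steered by arm.** The documents give no operator effect, resident share or steering rate, so all three are assumed: a resident-senior gap of 3-5 minutes, half of cases done by residents, and SD held at 5.

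Bias = share of balloon cases moved × gap. Type I error is taken at a true difference of 5 minutes, from the noncentral t with noncentrality bias/SE.

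| Balloon cases moved to senior operators | Bias (min) | Type I error, 16 per arm | Type I error, 20 per arm |
|---|---|---|---|
| None | 0 | 2.5% | 2.5% |
| One case (1/16 or 1/20) | 0.19-0.31 (16); 0.15-0.25 (20) | 3.2%-3.7% | 3.1%-3.6% |
| 12.5% | 0.38-0.63 | 4.0%-5.3% | 4.2%-5.8% |
| 25% (half of resident balloon cases) | 0.75-1.25 | 6.1%-10.1% | 6.7%-11.7% |

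A 25% shift the other way makes the test conservative. Type I error falls to 0.9%-0.4% and power from 78% to 64%-54% at 16 per arm; at 20 per arm the figures are 0.8%-0.3% and from 87% to 75%-64%.

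**What a covariate would do.** There are two candidates.

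- *Level planned before allocation.* The plan does not collect it, and the documents do not show that an operator is planned the day before. With 25% of balloon cases moved, 16 per arm and gaps of 3 and 5, adjusting for it leaves the bias at 0.75 and 1.25 minutes and type I error at 6.1% and 11.0%. It does not remove steering bias. Without steering, residual SD = √(25 − gap² × 0.25) = 4.77 and 4.33 at gaps of 3 and 5, and simulated power at 16 per arm is 80% and 87% against 78% unadjusted. At gaps of 0-1 minute power is about 77%, slightly worse than unadjusted. The gain needs a gap of about 2 minutes or more.
- *Level recorded at the D&E.* The plan already collects this. With 25% of balloon cases moved at random, adjusting for it brings the bias to about 0 and type I error to about 2.5% at 16 and 20 per arm. The level is settled after randomization, so this fails if switches follow case difficulty. It suits a sensitivity analysis, not the primary model.

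**The case for a change.** The best argument for a change is that the remedy is cheap and the exposure real. One sentence could say that arm is not a criterion for choosing the operator. The team can know the arm a day ahead, the operator acts directly on the outcome, and two moved cases out of 16 are enough to take type I error to 4% or more under the assumed gaps. Limiting residents to their last half-year narrows the range of experience but does not govern assignment. Recording the level is not the same as planning to use it.

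Much of this stands. The plan is silent on assignment, and the arithmetic is correct under its assumptions. But the harm needs a practice that no part of the document describes, and the same silence could be held against most unblinded trials of a procedure. A sentence on assignment would write down a policy without altering the design or the test, and a switch log or a by-arm table adds reporting. The covariate is an optional precision gain that depends on an operator gap the documents do not give.

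The missing analytic role is also not particular to operator level. No primary model is stated, so no variable has a role, and that lack cannot itself cause operator mix to depend on arm.

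**Conclusion.** No change is needed on this point. Followed as written, with operators chosen without regard to arm, the plan gives a test at its nominal one-sided 2.5%, and the 16 per group is unaffected. The bias scenario is possible, but it rests on three quantities absent from the documents: the operator gap, the resident share and the steering rate. Its illustrative size runs from about 3.1%-3.7% for a single steered balloon case to 10%-12% when half of resident balloon cases move in one direction with a 5-minute gap.

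The gap is one that analysts fill sensibly with data already collected: show actual operator level by arm and, if the arms differ, add a sensitivity analysis adjusted for it, noting that this level is fixed only after randomization. Evidence that operators were in fact assigned by arm would change this conclusion; the documents contain none.
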